Abbreviations: ACTH = adrenocorticotrophic hormone; ADA = anti-drug antibodies; AE = adverse event; C=Cycle; CT = computed tomography; ECG = electrocardiogram; ECOG PS = Eastern Cooperative Oncology Group performance status; FFPE = formalin-fixed paraffin-embedded; HBV = hepatitis B virus; HCV = hepatitis C virus; MRI = magnetic resonance imaging; PK = pharmacokinetics; RECIST = Response Evaluation Criteria in Solid Tumors; RNA = ribonucleic acid; TCR = T-cell receptor.

Table 11. Schedule of Activities: Combination F (F1: Avelumab plus CMP-001, F2: Avelumab plus CMP-001 and Utomilumab, F3: Avelumab plus CMP-001 and PF-04518600) – Safety and Efficacy Assessments (Phase 1b and Phase 2)

Protocol Activities	Screening ^[1]	Treatment												Post Treatment		
		CYCLE 1				CYCLE 2				CYCLES 3-23		CYCLES ≥24		End of Treatment/ Withdrawal ^[43]	Follow-Up (Day 30, Day 60, Day 90) ^[44]	Survival Follow Up
	≤28 Days prior to Randomization	Day 1	Day 8	Day 15	Day 22	Day 1	Day 8	Day 15	Day 22	Day 1	Day 15	Day 1	Day 15			
Visit Time Window (days)		(±) 2	(±) 2	(±) 2	(±) 2	(±) 2	(±) 2	(±) 2	(±) 2	(±) 2	(±) 2	(±) 7	(±) 7	(+) 7	(±) 3	
Informed Consent ^[2]	X															
Tumor History ^[3] , Medical History ^[4] , Baseline Signs & Symptoms ^[6]	X															
Randomization ^[18]		X														
Adverse Events ^[24] Concomitant Treatments ^[25]		Monitored and recorded continually														
Physical Examination ^[5]	X	X	X	X	X	X	X	X	X	X	X	As clinically indicated		X	X (Day 30)	
Vital Signs ^[8]	X	X	X	X	X	X	X	X	X	X	X	X	X	X	X (Day 30)	
ECOG PS ^[7]	X	X				X			X					X	X (Day 30)	
Contraceptive Check ^[9]	X	X				X			X		X		X	X	X (Day 90)	

Protocol Activities	Screening ^[1]	Treatment												Post Treatment		
		CYCLE 1				CYCLE 2				CYCLES 3-23		CYCLES ≥24		End of Treatment/ Withdrawal ^[43]	Follow-Up (Day 30, Day 60, Day 90) ^[44]	Survival Follow Up
	≤28 Days prior to Randomization	Day 1	Day 8	Day 15	Day 22	Day 1	Day 8	Day 15	Day 22	Day 1	Day 15	Day 1	Day 15			
Visit Time Window (days)		(±) 2	(±) 2	(±) 2	(±) 2	(±) 2	(±) 2	(±) 2	(±) 2	(±) 2	(±) 2	(±) 7	(±) 7	(+) 7	(±) 3	
Safety Labs/Measurements																
Hematology ^[10]	X	X	X	X	X	X	X	X	X	X	X	X	X	X	X (Day 30)	
Blood Chemistry ^[11]	X	X	X	X	X	X	X	X	X	X	X	X	X	X	X (Day 30)	
Coagulation ^[12]	X	As clinically indicated														
Serum/Urine Pregnancy Test ^[13]	X	X		X		X		X		X	X	X	X		X (Day 30)	
12-Lead ECG ^[14]	X	X				X								X		
HBV, HCV tests ^[15]	X															

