Serum for pharmacogenomic/ proteomic/metabolomic analysis ^[35]		X		X									
Plasma for pharmacogenomic/ proteomic/metabolomic analysis ^[36]	X	X										X	
PAXGene whole blood collection optimized for RNA analysis ^[37]	X	X		X		X	X	X				X	
Banked biospecimens ^[38]		X											
Blood for Anti-Qb antibodies ^[39]		X		X		X			X		X (C8 only)		
Blood for Avelumab immunogenicity (ADA) testing ^[40]		X				X			X		X (C6 and C10 only)		

Protocol Activities	Screening ^[1] ≤28 days prior to Randomization	On Treatment (1 Cycle=28 days)									Post Treatment		
		Cycle 1				Cycle 2		Cycle 3	Cycle 4	Cycle 5	Cycles 6, 8, 10	End of Treatment /Withdrawal [43]	Follow Up (Day 30, 60, 90) [44]
		Day 1	Day 8	Day 15	Day 22	Day 1	Day 15	Day 1	Day 1	Day 1	Day 1		
Blood for utomilumab immunogenicity (ADA) testing ^[41] (Combination F2)		X				X			X		X (C6 and C10 only)		
Blood for PF-04518600 immunogenicity (ADA) testing ^[42] (Combination F3)		X				X			X		X (C6 and C10 only)		

Footnotes for Schedule of Activities (Combination F)

1. **Screening:** To be obtained within 28 days prior to randomization.
2. **Informed Consent:** Must be obtained prior to undergoing any study-specific procedure.
3. **Tumor History:** To be collected within 28 days prior to randomization. Includes disease characteristics, information on prior regimens (including dosing and duration of administration, best response observed, and recurrence date), surgery, and radiation therapy.
4. **Medical History:** To be collected during the screening period. Includes history of diseases other than the primary tumor under consideration (active or resolved) and concomitant illnesses.
5. **Physical Examination:** Includes an examination of major body systems. Weight for the purposes of dose calculation will be recorded at screening and within 3 days pre-dose Day 1 of each cycle. Weight will not be collected at End of Treatment. Height will be measured at screening only. During treatment starting C24 D1 physical examination to be performed only when clinically indicated.
6. **Baseline Signs/Symptoms:** Patients will be asked about any signs and symptoms experienced within the 14 days prior to study entry (Study entry is defined as randomization date) and recorded on the Medical History case report form (CRF) page. During treatment any new or worsening conditions since baseline should be reported on the Adverse Event (AE) CRF.
7. **ECOG PS:** ECOG performance scale is available as [Appendix 2](#).

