24. **Adverse Event (AE) Assessments:** Adverse events should be documented and recorded at each visit using National Cancer Institute (NCI) Common Terminology Criteria for Adverse Events (CTCAE) version 4.03. For serious adverse events (SAEs), the active reporting period to Pfizer or its designated representative begins from the time that the patient provides informed consent, which is obtained prior to the patient's participation in the study, ie, prior to undergoing any study-related procedure and/or receiving investigational product, through and including 90 calendar days after the last administration of the study treatment. SAEs occurring to a patient after the active reporting period has ended should be reported to the sponsor if the investigator becomes aware of them; at a minimum, all SAEs that the investigator believes have at least a reasonable possibility of being related to study treatment are to be reported to the sponsor. AEs serious or non-serious, suspected to be related to the study treatment based on investigator's assessment, should be recorded on the CRF. If a patient begins a new anticancer therapy, the AE reporting period for non-serious AEs ends at the time the new treatment is started. Death must be reported if it occurs during the SAE reporting period after the last dose of study treatment, irrespective of any intervening treatment (see [Section 8.2](#)).

25. **Concomitant Treatments:** Concomitant treatments will be recorded from 28 days prior to the start of study treatment and up to 90 days after the last dose of investigational products. All concomitant medications should be recorded in the CRF including supportive care drugs (eg, anti-emetic treatment and prophylaxis), and the drugs used to treat AEs or chronic diseases, and non-drug supportive interventions (eg, transfusions). Concomitant treatments will not be collected for patients who initiate subsequent anticancer therapy.

26. **Subsequent Anti-Cancer Treatment:** Subsequent anticancer therapy will be documented and recorded for patients who discontinue investigational products and continue in follow up, and during survival follow up.

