8. ADVERSE EVENT REPORTING

8.1. Adverse Events

All observed or volunteered AEs regardless of treatment group or suspected causal relationship to the investigational product(s) will be reported as described in the following sections.

For all AEs, the investigator must pursue and obtain information adequate both to determine the outcome of the AE and to assess whether it meets the criteria for classification as an SAE requiring immediate notification to Pfizer or its designated representative. For all AEs, sufficient information should be obtained by the investigator to determine the causality of the AE. The investigator is required to assess causality. Follow-up by the investigator may be

required until the event or its sequelae resolve or stabilize at a level acceptable to the investigator, and Pfizer concurs with that assessment.

As part of ongoing safety reviews conducted by the sponsor, any non-serious AE that is determined by the sponsor to be serious will be reported by the sponsor as an SAE. To assist in the determination of case seriousness, further information may be requested from the investigator to provide clarity and understanding of the event in the context of the clinical study.

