8.2. Reporting Period

For SAEs, the active reporting period to Pfizer or its designated representative begins from the time that the subject provides informed consent, which is obtained prior to the subject's participation in the study, ie, prior to undergoing any study-related procedure and/or receiving investigational product, through and including 90 calendar days after the last administration of the study treatment.

SAEs occurring to a subject after the active reporting period has ended should be reported to the sponsor if the investigator becomes aware of them; at a minimum, all SAEs that the investigator believes have at least a reasonable possibility of being related to study treatment are to be reported to the sponsor.

AEs (serious and non-serious) should be recorded on the case report form (CRF) from the time the subject has taken at least 1 dose of study treatment through 90 calendar days after the last administration of the study treatment.

If a patient begins a new anticancer therapy, the AE reporting period for non-serious AEs ends at the time the new treatment is started. Death and SAE must be reported if it occurs during the SAE reporting period after the last dose of study treatment, irrespective of any intervening treatment.

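### The AE footnotes in all five Schedules of Activities tie CRF recording to suspected relatedness, contradicting Section 8.2, which they cite, and Sections 7.1.3, 8.1 and 8.14.2

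*Protocol*

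**What the plan says.** The AE footnote is essentially the same in each Schedule of Activities. Its CRF sentence asks for the recording of "AEs serious or non-serious, suspected to be related to the study treatment", as assessed by the investigator. It gives no time window, and the footnote ends by referring the reader to Section 8.2.

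Section 8.2 says: "AEs (serious and non-serious) should be recorded on the case report form (CRF) from the time the subject has taken at least 1 dose", and continues the window to 90 calendar days after the last administration. It states no causality condition. Section 8.1 makes the scope explicit: "All observed or volunteered AEs regardless of treatment group or suspected causal relationship to the investigational product(s) will be reported". Section 7.1.3 sends AEs occurring during the study to the AE page of the CRF, and Section 8.14.2 says the same of all AEs. Section 8.9 requires a causality assessment for every AE, serious or not.

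The Schedules also contain broader wording. The AE footnote opens with "Adverse events should be documented and recorded at each visit". Footnote 6 in every Schedule says "During treatment any new or worsening conditions since baseline should be reported on the Adverse Event (AE) CRF". The AE row of the tables reads "Monitored and recorded continually".

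Section 9.6.2.1 plans the number and percentage of patients with any AE, any SAE, any treatment-related AE and any treatment-related SAE, by worst toxicity grade.

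**The concern.** Site staff work from the Schedule of Activities. A coordinator who takes the CRF sentence at face value would enter the events the investigator suspects are related and could leave the others off. That would feed directly into Section 9.6.2.1, where the all-causality tables are meant to stand beside the treatment-related ones. If unrelated-rated events are missing at some sites, the two sets of tables move towards each other for a reason that has nothing to do with the drugs.

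All-causality counts matter here because the study is open-label and two or three investigational agents are given together, which makes attribution by the investigator uncertain. An event never entered because it was first judged unrelated is hard to reconsider when the safety profile becomes clearer. Section 3.3 provides for just such reconsideration: it lets an unlisted AE, or one outside the observation period, be defined as a DLT later.

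**Working it through.** No sample size, power or error-rate formula applies. The check sets the instructions side by side.

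| Place | Which AEs | Window stated |
|---|---|---|
| AE footnote, CRF sentence (A, B, C fn 22; D fn 23; F fn 24) | Suspected related | None |
| AE footnote, opening sentence | All | Each visit |
| Footnote 6, all Schedules | Any new or worsening condition | During treatment |
| AE row of the tables | All | Continual |
| Section 7.1.3 | All | During the study |
| Section 8.1 | All, regardless of causality | Refers onward |
| Section 8.2 | All | First dose to 90 days after last dose |
| Section 8.14.2 | All | None |

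1. Only the CRF sentence in the footnotes carries a relatedness condition on what is entered. Every other instruction in the table is broader.

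2. Could the condition belong only to the late period? The sentence before it concerns SAEs after the active reporting period, where the floor is "at a minimum, all SAEs that the investigator believes have at least a reasonable possibility of being related to study treatment". However, the footnote and Section 8.2 run in the same order: SAE active period, SAEs after that period, CRF recording, new anticancer therapy, death. The conditional sentence stands exactly where Section 8.2 has its unconditional one. It also covers non-serious AEs, which the sentence before it does not, and nothing in it limits it to the late period. The wording does not support a late-period-only reading.

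3. Section 8.9 asks for causality on every AE, which presupposes that unrelated AEs are captured. The condition conflicts with this as well.

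4. What is not touched. SAE reporting to the sponsor, from consent to 90 days after the last dose, carries no causality condition in either the footnotes or Section 8.2. The treatment-related summaries rest on the events that the sentence does ask for. DLTs under Section 3.3 are AEs attributable to study treatment, so they are not directly affected.

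5. Which tables are exposed. Section 1.2.5.3 gives patient counts for any treatment-emergent AE and any treatment-related one in the CMP-001 studies. If only related events were entered, the first count would fall to the second:
- CMP-001-001: 112 of 113 (99.1%) against 109 of 113 (96.5%), a difference of 3 patients.
- CMP-001-002: 18 of 18 (100%) against 16 of 18 (88.9%), a difference of 2.
- CMP-001-003: 12 of 13 (92.3%) against 12 of 13 (92.3%), no difference.

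The overall percentage hardly moves in the largest study. A by-grade count can move more: in CMP-001-003, Grade 3 or higher events occurred in 8 of 13 patients (61.5%) and related ones in 4 of 13 (30.8%). These figures come from other trials and show only where the exposure lies. They do not forecast this trial.

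**The case against.** The best defence is that the protocol as a whole is clear. The Schedule calls itself an overview and sends the reader to the Assessments section for detail; that section and Section 8 require all AEs. The word only does not appear in the sentence. The same footnote opens without a causality limit, footnote 6 sends any new or worsening condition to the AE CRF, and the table row is unrestricted. Events of unknown causality are handled as related for reporting (Section 8.9), and suspected immune-related AEs are reported under the Section 8 rules (Section 8.1.1). The 90-day follow-up is also in the Schedules, through the follow-up footnote.

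Much of this stands. A reader might infer that the Schedules tell sites to record only related AEs and that the all-causality rates would therefore be incomplete. The documents do not support that: the restriction is an inference from one sentence, and several others point the other way. A reader might also compare the background fatigue rates, all-causality against related, and expect a large shrinkage: 33.3% against 18.5% and 26.8% against 12.2% (PF-04518600, Section 1.2.3.4.1), and 43.5% against 34.8% (utomilumab plus pembrolizumab, Section 1.2.2.4.1). This does not hold up either. The ratios run from 1.25 to 2.2 for a single term, the summary in Section 1.2.3.4.1 describes the same 33.3% and 26.8% as related, and the any-AE counts above barely differ in the largest CMP-001 study.

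The defence does not remove the contradiction. A sentence on what to enter on the CRF conflicts with the section it cites, in five places.

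**Conclusion.** The point holds as an internal inconsistency in an operational rule. The design is all-causality collection, and the footnotes misstate it. All-causality AE summaries could, not would, be under-recorded, and only where a site applies the footnote sentence literally. The loss would fall mainly on non-serious AEs judged unrelated, and would show in by-term and by-grade tables more than in the overall any-AE percentage.

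No size can be attached to this. The documents do not say how sites read the footnote, or what share of AEs in this trial is judged unrelated. The conclusion rests on the text alone and applies to all five Schedules, not just Combination F.

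**What to change.** In the AE footnotes of all five Schedules, remove the relatedness condition and use the Section 8.2 rule: all AEs, serious and non-serious, go on the CRF from first dose through 90 days after the last dose, with recording of non-serious AEs ending at the start of new anticancer therapy. If the sponsor meant the condition for events after the 90-day period, keep it as a separate sentence that says so, so that no instruction on late related events is lost.

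Send sites a clarification letter now and carry the wording into the next amendment. The cost is administrative, plus some extra data entry at any site that has been using the narrower reading. Objectives, sample size and planned analyses do not change.

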1. INTRODUCTION

This is a Phase 1b/2 dose-finding study to evaluate safety, pharmacokinetics (PK), pharmacodynamics (PD), and preliminary antitumor activity of avelumab (MSB0010718C), a programmed death-ligand 1 (PD-L1) monoclonal antibody (mAb) in combination with other cancer immunotherapies in patients with locally advanced or metastatic solid tumors (eg, non-small cell lung cancer [NSCLC], melanoma, squamous cell carcinoma of the head and neck [SCCHN]), and triple-negative breast cancer [TNBC]). Avelumab reversal of T cell inhibition via PD-L1 is only one potential mechanism which can augment anti-tumor immunity and it appears that in many patients simply blocking this resistance pathway is insufficient to trigger a robust anti-tumor response. As detailed in this protocol, mouse tumor modeling suggests that combining avelumab with 4-1BB or OX40 agonist mAbs as doublets leads to increased anti-tumor activity compared with mice treated with any of the single agents. In addition, macrophage-colony stimulating factor (M-CSF) blocking antibodies when combined with 4-1BB agonist mAbs and avelumab as a triplet in models where myeloid suppressive cells may be important exhibits greater anti-tumor tumor activity than the respective doublets. Furthermore, triplet combinations of 4-1BB and OX40 agonist mAbs showed a marked increase in anti-tumor activity in these models compared with the respective doublets. It is thought that triplets may be more effective compared with doublets as it is likely that doublet therapies, while potentially effective, do not address mechanisms of immune homeostasis as well as select triplets. Therefore, after the evaluation of respective doublets in this study for safety and preliminary clinical activity, triplet combinations may be explored in specific clinical settings where these combinations might be more effective.

While the above combinations address mechanisms thought to be active in tumors harboring a pre-existing immune response, they do not address the growing unmet medical need of patients who progress on PD-1/PD-L1 therapy due to absent or inactive immune responses. Preclinical studies detailed in this protocol suggest a Toll-like Receptor 9 (TLR9) receptor agonist may initiate immune responses that could be further enhanced by a PD-L1 pathway inhibitor in settings where single agent inhibition of the PD-L1 pathway is less effective. These preclinical studies also support the hypothesis that 4-1BB and OX40 agonist mAbs may further activate T cell responses activated by the TLR9/PD-L1 combination.

The primary purpose of this study is to assess the safety and early signs of efficacy of the above mentioned avelumab doublet combinations followed by the evaluation of a triplet combination of these agents based on the safety of the respective doublets. The proposed combinations are as follows:

- Combination A: avelumab plus utomilumab, a fully human immunoglobulin (Ig) G2 isotype mAb agonist of 4-1BB (CD137, TNFRSF9) that promotes survival and function of T cells, especially CD8+ T cells.
- Combination B: avelumab plus PF-04518600, a fully human IgG2 mAb agonist of OX40 (CD134) that promotes survival and function of T cells, especially CD4+ T cells.

- Combination C: avelumab plus PD 0360324, a fully human IgG2 mAb directed against M-CSF that may inhibit tumor infiltration by immunosuppressive macrophages. (Sites in the United Kingdom [UK] will not participate in this combination).
- Combination D: avelumab plus utomilumab and PF-04518600 that is expected to provide complementary support for CD8+ and CD4+ T cells.
- Combination F: avelumab plus CMP-001, an encapsulated TLR9 agonist that is expected to activate tumor-infiltrating plasmacytoid dendritic cells (pDCs) leading to activation and recruitment of anti-tumor T-cells to the tumor microenvironment. CMP-001 is expected to elicit T cell priming and infiltration into the tumor microenvironment, whereas avelumab is expected to block T cell inhibition by PD-L1 that is induced by CMP-001. Utomilumab or PF-04518600 will be evaluated in combination with avelumab and CMP-001 for the promotion of survival and function of T-cells activated by the combination. (Only sites in the United States [US] will participate in this combination).

Additional combinations of avelumab with other immune modulators may be incorporated into this protocol, based on emerging preclinical and clinical data.

1.1. Indication

Avelumab is a fully human anti-PD-L1 mAb of the Ig G1 isotype that is currently being investigated in combination with other cancer immunotherapies to enhance anti-tumor activity over that expected by avelumab alone in patients with locally advanced or metastatic solid tumors. Avelumab is expected to increase the effectiveness of anti-tumor T cells by preventing inhibition of T cell activation. This effect is expected to be enhanced by agents that promote anti-tumor immunity by complementary mechanisms such as promotion of T cell survival or removal of inhibitory myeloid cells.

1.2. Background and Rationale

1.2.1. Avelumab

Avelumab selectively binds to PD-L1 and competitively blocks its interaction with programmed death protein-1 (PD-1). Compared with anti-PD-1 antibodies that target T-cells, avelumab targets tumor cells and therefore expected to have fewer side effects, including a lower risk of autoimmune-related safety issues, as blockade of PD-L1 leaves the programmed death-ligand 2 (PD-L2)/PD-1 pathway intact to promote peripheral self-tolerance.¹ For complete details of the in vitro and nonclinical studies, refer to avelumab Investigator's Brochure (IB).²

1.2.1.1. Avelumab Clinical Experience

[figure not shown]
Avelumab is being developed jointly by Pfizer and Merck KGaA/EMD Serono, and is being studied in Phase 1, 2, and 3 clinical protocols in a wide variety of cancers, including non-small cell lung cancer, gastric cancer, Merkel cell carcinoma (MCC), renal cell

carcinoma (RCC), ovarian cancer, urothelial cancer, and Hodgkin's Lymphoma, as single agent or in combination with chemotherapy, tyrosine kinase inhibitors (TKIs), or other immune-modulating agents.

CCI

CCI

CCI

CCI

CCI

CCI

CCI

[figure not shown]
CCI

CCI

[figure not shown]
CCI

CCI

[figure not shown]
CCI

[figure not shown]
CCI

CCI

CCI

CCI

CCI

CCI

CCI

CCI

